### 4. Site Descriptions and Targets

The two clinical sites include the 1) University of North Carolina at Chapel Hill (UNC-CH) and 2) Division of Pediatric Endocrinology and Diabetes at Stanford University. Both clinical sites are well-established academic medical centers with vast experience in diabetes translational research. UNC-CH will also oversee coordination of the SMART pilot. Northwest Lipid Research Laboratory in Seattle, Washington will complete the required laboratory (blood sample) analysis for the SMART Pilot. **COVID-19 PROVISIONS:** *Due to ramifications of the COVID-19 Pandemic, we are no longer able to have samples assayed with Northwest Lipid Metabolism and Diabetes*

*Research Laboratories in Seattle, Washington. We will be using the Diabetes Diagnostic Laboratory at the University of Missouri. Existing specimens stored at the Northwest Research Laboratories will be transferred to the Stanford University School of Medicine for storage.*

**Participant Recruitment: Stanford:** The recruitment goal for Stanford will be 42 participants (~ 4/month over 12 months). Among the current patient population at Stanford, approximately 300 are between the ages of 19-30 and meet study inclusion criteria for weight and HbA1c.

**Participant Recruitment: UNC:** The recruitment goal for UNC is 42 (~4/month over 12 months). The number of patients in the UNC Health Care System who meet our inclusion criteria is approximately 150 and in addition, the UNC Student Health center follows about 100 T1D patients. If necessary, UNC-CH may also recruit from T1D patients seen at the nearby Duke Diabetes clinic.

Only those participants who withdraw from the trial *before randomization* will be replaced.

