## 11. Statistical Considerations

We will primarily compare the 3-month response rates to each of the three initial diets using standard statistical comparison procedures (e.g., t-tests and ANOVA) for differences in glycemic control (HbA1c and percent time in hypoglycemia) and change

in weight. In addition, we will conduct a series of secondary, hypothesis-generating analyses using standard statistical approaches as well as more complex fixed and mixed effect regression methods such as generalized additive models and random forests for these outcomes plus body fat and fat free mass. We will compare all diet sequences (there are 12) using the same outcomes and will incorporate evaluation of measures of ingestive behaviors. After adjusting for multiple comparisons, the proposed sample size of n=84 is sufficient to ensure 60% power to detect a moderate effect size (Cohen h=0.68) and 80% to detect a large effect size (Cohen h=0.85) at a significance level of 0.10 for comparing response rates among the 3 diets. Based on data reported in Wing et al (2016) and Russell et al (2014) and other preliminary data, we estimate for the same significance level and with 80% power that we will be able to detect a difference of about 3.0kg for weight change, 1.3% for HbA1c change, and 1.3 percentage point change in percent time <70mg/dl. Here we emphasize that, by design, our primary goal for this pilot work is to inform the final efficacy design, and we have therefore not designed this pilot SMART to be fully powered for all analyses.

An advantage of SMARTs is that they allow for efficient estimation of precise (i.e., deeply tailored) diet strategies. A precise diet strategy adapts treatment to the evolving health status of each participant. We will use a regression-based approximate dynamic programming algorithm known as Q-learning to estimate the precise diet strategy that maximizes weight loss while improving suboptimal or maintaining good glycemic control over the duration of the trial. The form of this estimated optimal diet strategy will generate hypotheses about how best to choose and adapt diets to individual patients. This will require the use of SMART analysis methods for balancing competing outcomes.

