Statistical Analysis Plan

ACT1ON Phase 2 (SMART Pilot) and Phase 3 (Efficacy Trial Development)

NCT03651622

January 20th, 2022

Analytic approach: The overarching objective of this study was, in addition to comparing three dietary approaches for co-management of glycemia and weight among young adults with type 1 diabetes, to identify individual-level characteristics that might drive response to a particular diet approach. Due to the COVID-19 pandemic, we recruited n=68 instead of the planned n=72 study participants, which led to the following changes in our analytic plan:

The updated analytic plan consists of the following descriptive and modeled approaches:

- Pre-COVID diet period 1 (Randomization 1): Model outcomes using generalized linear models (PROC GLM) in SAS due to lack of repeated measures
- All data, both pre- and post-COVID: Generalized estimating equations (PROC GEE) in SAS accounting for repeated measures
- Response variables for all models: Change for each of three diet periods for each of the primary and secondary outcomes:
 - o Primary outcomes:
 - Weight (kg)
 - Hemoglobin A1c (%)
 - Percent time in clinical hypoglycemia (54-60 mg/dL)
 - o Secondary outcomes:
 - Body fat percentage
 - Percent time in target glucose range (70-180 mg/dL)

Pre-COVID, diet period 1 (Randomization 1) only:

- Descriptive analysis
 - o Change in primary and secondary outcomes for each diet period *irrespective of diet* (PROC MEANS in SAS), paired t-test for overall changes in outcomes.
 - o Examine change in primary and secondary outcomes separately for each diet assignment in each of the three diet periods (PROC MEANS in SAS, paired t-test for each diet).
- Modeled analysis (PROC GLM in SAS)
 - o Change in primary and secondary outcomes for pre-COVID diet period 1 according to randomized diet assignment, and adjusted for site, baseline level of the outcome, and gender, which was imbalanced across diet assignments at baseline. Use this model to test for differences between diets.

All data, both pre- and post-COVID:

- Descriptive analysis

- Change in primary and secondary outcomes for each diet period (i.e., each randomization) *irrespective of* diet (PROC MEANS), paired t-test for overall change in outcomes
 - Examine change in primary and secondary outcomes separately for each diet in each of the three diet (i.e., randomization) periods (PROC MEANS, paired t-test for each diet) and look at mean differences between diets (PROC MEANS).

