 - Examine change in primary and secondary outcomes separately for each site and each gender in each of the three diet (i.e., randomization) periods (PROC MEANS, paired t-test for change within each stratum per diet period).
- Modeled Analysis (PROC GEE in SAS)
- Change in primary and secondary outcomes between diet periods (i.e., randomization periods) accounting for diet assignment and adjusted for site, the baseline level of the outcome, duration (months) between each diet period given that duration varied widely during the pandemic, a COVID indicator (yes/no), diet period (1, 2, or 3), and gender.

Planned analysis: consider analytic approaches that will allow for identification of individual-level characteristics that may predict individual response to a given diet assignment.

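### In the all-data analyses, HbA1c and weight changes that straddle the April 2020 switch mix two measurement methods, and neither the paired t-tests nor the uncoded COVID term reliably allows for it (minor, cheap to fix)

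*SAP*

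**What the plan says.** **Measurement.** The protocol's summary table of COVID-19 provisions moves HbA1c from in-person collection to home kits, and weight from the study visit to the BodyTrace scale at home. Section 4 replaces the Seattle laboratory: "We will be using the Diabetes Diagnostic Laboratory at the University of Missouri". Section 8a confirms both changes from the virtual transition. Specimens held in Seattle go to storage. Neither document describes re-assay, bridging or calibration. The Version 6 amendment promises only that the analysis will allow for longer time on a diet.

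**Analysis.** In the SAP the response in every model is the change over a diet period. The all-data descriptive block uses a "paired t-test for overall change in outcomes", repeats it per diet, and adds a "paired t-test for change within each stratum per diet period" for site and gender. None of these is split by COVID status or method. The all-data GEE adjusts for site, baseline level, duration and "a COVID indicator (yes/no), diet period (1, 2, or 3), and gender". It does not say what makes a period a yes.

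**Diet test.** A separate block is headed "Pre-COVID, diet period 1 (Randomization 1) only". Of its linear model the SAP says: "Use this model to test for differences between diets".

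**The concern.** If the old and new methods differ by a constant, that constant cancels when both visits of a period use the same method. It enters in full when the first visit used the old method and the second the new one. There are therefore three kinds of period: old-old, old-new and new-new.

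The pooled paired t-tests treat the three alike. A yes/no term coded by whether the period ends after the switch groups old-new with new-new. Coded by whether it starts after the switch, it groups old-new with old-old. Either way, part of the offset stays in the straddling periods. A calendar definition of COVID could also miss the method change, because the Version 6 amendment of 19 March 2020 still kept the HbA1c draw and physical measures in person. Duration adjusts for time, not for method.

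What is at stake is the per-diet estimate of change in weight and glycemic control, which Section 3 of the protocol wants in order to inform the full trial.

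**Working it through.** The plan gives no figure on this point, so there is none to reproduce.

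**1. Share of straddling periods (assumed).**
- Visit spacing is about 3.5 months: the Appendix 1 timeline has visits at -14 days and at 3, 6.5 and 10 months.
- The Version 2 log of August 2018 has recruitment starting in September. I assume even enrolment from September 2018 to the switch, 18.7 to 19 months. A log entry is only indicative of the real dates.
- Share per period = gap / enrolment window: 3.5/19 = 0.184; 3.5/18.7 = 0.187.
- With the SAP's n = 68 and complete follow-up: 68 x 0.184 = 12.5 and 68 x 0.187 = 12.7, so about 13 participants per period.

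**2. Bias of a pooled mean change = share x offset.** The offsets are assumptions, and the sign is unknown.

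| Outcome | Assumed offset | Bias |
|---|---|---|
| HbA1c | 0.1 to 0.3 points | 0.184 x 0.1 = 0.018 to 0.187 x 0.3 = 0.056 points |
| Weight | 0.5 to 1.0 kg | 0.184 x 0.5 = 0.092 to 0.187 x 1.0 = 0.187 kg |

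**3. Scale.** Section 11 says the pilot can detect "a difference of about 3.0kg for weight change, 1.3% for HbA1c change". The upper biases are 0.056/1.3 = 4% and 0.187/3.0 = 6% of these. Those figures concern differences between diets, so the standard error of a mean change is a fairer yardstick.
- SD backed out of Section 11, assuming 24 per arm (the SAP's planned 72) and a two-sided level of 0.10/3: difference / [(0.842 + 2.128) x sqrt(2/24)] = difference / 0.857. This gives 3.0/0.857 = 3.5 kg and 1.3/0.857 = 1.5 points.
- SE at n = 68: 3.5/sqrt(68) = 0.42 kg; 1.5/sqrt(68) = 0.18 points.
- With the share rounded to 0.19, the bias is 0.10 to 0.31 SE for HbA1c and 0.22 to 0.45 SE for weight. A nominal 5% paired test then has an actual error rate of 5.1 to 6.1% and 5.6 to 7.3%.

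**4. What each coding does.** I simulated a least-squares stand-in for the GEE mean model: 3,000 runs, n = 68, three periods, HbA1c offset 0.3. Entries are mean fitted coefficients of the COVID term.

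| Coding | No pandemic effect | Pandemic effect 0.2 |
|---|---|---|
| Truth: old-new; new-new | 0.30; 0 | 0.50; 0.20 |
| Yes if period ends after switch | 0.16 | 0.37 |
| Yes if period starts after switch | -0.10 | 0.07 |
| Yes if period straddles | 0.31 | 0.46 |
| Three-level: old-new; new-new | 0.30; -0.02 | 0.51; 0.21 |

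**5. Diet contrasts.** A second simulation covered 72 settings of 150 runs each: n = 68, the 12 regimes in blocks of 24, and enrolment over 12 or 19 months. Response, dropout, prolongation of straddling periods and working correlation were varied. As a fraction of the offset, the error in a diet contrast had mean -0.007 to 0.009 and SD 0.035 to 0.087 under start or end coding. It was zero under straddling-only or three-level coding. The largest SD is 0.087 x 0.3 = 0.026 points, or 0.087 x 1.0 = 0.087 kg.

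Unadjusted mean differences between diets in one period are open to chance imbalance. With 23 per diet, the SD of the difference in straddling share is sqrt(2 x 0.19 x 0.81/23) = 0.116. The 95% range is then 1.96 x 0.116 x 0.3 = 0.07 points, or 1.96 x 0.116 x 1.0 = 0.23 kg, centred on zero.

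**The case against.** **No harm to the diet test.** The model named for testing diets uses pre-COVID period 1 only, and Section 11 of the protocol bases effect sizes on 3-month means. This stands. A reader might infer that the switch biases the diet comparison. The documents do not support that: the switch date is unrelated to the randomized diet, and step 5 shows contrasts hardly move.

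**A binary term could suffice.** A reader might infer that no yes/no coding can deal with the offset. That goes too far. A flag for straddling periods alone absorbs it. What such a flag loses is the distinction between old-old and new-new, which concerns a real pandemic effect and not measurement. The point is that the SAP does not say which coding it means.

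**The size is assumed.** This stands. The offset could be zero. A larger share, 3.5/12 = 0.29, is tempting because Section 4 speaks of 12 months of recruitment. Twelve months from September 2018 would end in 2019, too early for any period 1 to reach April 2020. The amendment logs also show enrolment still open in early 2020. So 0.29 in every period does not fit the dates.

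**Not all primary outcomes are equally exposed.** A reader might extend the point to CGM. There only the person inserting the sensor changed, and one device is named throughout, so the case is much weaker.

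**The GEE recoding leaves the paired tests as they are.** This is correct. Splitting every t-test by period type would also leave about 13/3, or 4, straddlers per diet and period. The fix below takes both into account.

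Whether the pre-COVID block already gives same-method summaries for periods 2 and 3 is unclear: despite its heading, one bullet asks for change "separately for each diet assignment in each of the three diet periods". That conflict, and the labelling of body fat after DXA stopped, are separate editorial points.

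**Conclusion.** The point holds as a minor improvement. The all-data overall and within-diet mean changes in HbA1c and weight carry a bias equal to the straddling share times any method offset. The paired t-tests make no allowance for it. The GEE removes it only if the yes/no term happens to flag exactly the straddling periods.

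The bias is about 0.02 to 0.06 HbA1c points and 0.09 to 0.19 kg, under half a standard error of the overall mean change. These figures rest on assumed offsets of 0.1 to 0.3 points and 0.5 to 1.0 kg, and on even enrolment from September 2018 to the switch. The estimates affected are mainly descriptive, and the diet test is not in question.

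**What to change.** 1. For HbA1c and weight, code each period by the measurement method actually used at its two visits, not by calendar date. Replace the yes/no COVID term with a three-level factor: old-old, old-new, new-new. State that the old-new coefficient also carries pandemic-onset effects and is not a pure method effect.
2. Add one sensitivity run, leaving out straddling periods, of the GEE and of the overall and per-diet mean changes. This is the part that addresses the paired t-tests. Do not add straddling-only t-tests in small strata.
3. Section 9b gives participants the transmitting BodyTrace scale at run-in. Where pre-switch readings exist, compare them with the clinic weights to check the weight offset directly.

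**Cost.** SAP wording and one degree of freedom in the GEE. In the simulations the SE of a diet contrast rose by 0.2 to 0.5% against the yes/no term. The sensitivity run drops about 18 to 19% of changes per period, leaving about 55 of 68. That alone widens standard errors by about 11% (1/sqrt(1 - 0.187) = 1.11); the simulated range for a GEE diet contrast, over both enrolment windows, was 9 to 27%. It should therefore stay a sensitivity run. No new data are needed.

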Study Design	
This is an initial pilot and feasibility study using a Sequential, Multiple Assignment, Randomized Trial (SMART) design to identify acceptable and effective dietary strategies to optimize both glycemic control and weight management. This pilot study will be done at UNC and Stanford.
 
Sequential randomization will occur following the baseline, 3 months, and 6 months. Following the baseline data collection and a short run-in period, participants will be randomized to one of the three diets (stratified by site with block size of 4). Using a priori decision rules following the 3 and 6 month visit post-initial randomization, those for whom the diet assigned is not acceptable or is not effective will be re-randomized. A total follow-up time of 10.5 months allows for evaluation of the effect of the diets on initial weight loss and on early maintenance of initial weight loss. The decision criteria for re-randomization will incorporate both clinical outcomes (glycemic control and weight change) and acceptability of the diet to the participant.

Subject Population Key Criteria for Inclusion and Exclusion	
Inclusion Criteria
 
 
1. Individuals ages 19-30 years old
 
2. History of type 1 diabetes for greater than one year
 
3. HbA1C less than 13% within the last 6 mos.
 
4. BMI of 27-39.9 at time of phone screening
 
 
Exclusion Criteria
 
The study will exclude based on the following criteria:
 
 
1. Individuals with other metabolic disorders, diagnosed eating disorder, prohibitive strict dietary restrictions, or those with other serious condition that renders participation inappropriate.
 
2. Individuals that have experienced DKA or severe hypoglycemia requiring outside assistance in the last 6 months.
 
3. Females who are pregnant, breast feeding, planning to become pregnant during the study period or delivered a baby in the last 12 months
 
4. Individuals unwilling to follow any of the three study diets.
 
5. Individuals who are unwilling to monitor blood glucose at least three times a day.
 
6. Individuals who have lost 10 or more pounds in the last 6 months.
 

Number of Randomized Subjects	
84 randomized subjects (42 at UNC, 42 at Stanford) Participants withdrawn from the study before randomization will be replaced.

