We also note that there are 21 possible diet sequences, but there are only 12 treatment regimes based on the randomization scheme. The distinction between regimes and sequences is described in Chapter 2 of *Adaptive Treatment Strategies in Practice: Planning Trials and Analyzing Data for Personalized Medicine* (Kosorok and Moodie, 2016), but this can be illustrated by example. One treatment regime is the following: treat initially with Diet 1, then, if the patient responds favorably after 3 months, continue with the same diet, otherwise switch to Diet 3. After 6 months, if the patient responds favorably, continue with the same diet as given in the previous period. Otherwise, if they were on Diet 1, switch to Diet 3; If they were on Diet 3, switch to Diet 2. Although this is a single treatment regimen (reflecting a single treatment choice at each decision time), this regime is consistent with the following four treatment paths: (1) if the patient responds favorable at both time points, they will experience Diet 1 repeated three times. (2) If they respond favorably at 3 months but not at 6 months, then their diet sequence would be Diet 1, Diet 1, and Diet 3. (3) If they responded unfavorably at 3 months but favorable at 6 months, then their diet sequence would be Diet 1, Diet 3, Diet 3. (4) If they respond unfavorably at both 3 and 6 months, their diet sequence would be Diet 1, Diet 3, and Diet 2. The issue is that a regime focuses on the decision a clinician can make either initially, or when the patient experiences an unfavorable response, at either 3 or 6 months. The remaining decisions are made automatically since favorable responses do not lead to changes in diet. Note that this means that some diet sequences are consistent with more than one treatment regime, and thus the data from same patients will sometimes be used for estimating more than one of the 12 regimes. With balanced randomization, at least 6 patients will be assigned to each treatment regime.

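### The SAP names no regime or Q-learning analysis although the protocol plans both, and its all-period diet comparison pools participants who stayed on a diet with those who switched

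*SAP*

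**What the plan says.** **Protocol, Section 11.** Beyond the 3-month comparison of starting diets, the protocol plans three analyses that depend on the sequential design:

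- A 12-way comparison: "We will compare all diet sequences (there are 12) using the same outcomes". Later in the same section: "We also note that there are 21 possible diet sequences, but there are only 12 treatment regimes". The section lists the 12 regime codes, explains that each allows four paths depending on response, and says that one participant's data may serve more than one regime. It gives no estimator and no weights.
- Q-learning with three regression models (baseline, 3 months, 6 months) that include past diets.
- A 9-month intent-to-treat comparison by starting diet.

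**SAP.** The SAP reports that "we recruited n=68 instead of the planned n=72 study participants" and says that this led to an updated plan. That plan contains a GLM for pre-COVID period 1, descriptive changes by diet in each of the three periods, and a GEE over all periods. The GEE terms are diet, site, baseline outcome, duration, COVID indicator, period and gender. No regime, weight, response status, previous diet or diet-by-characteristic term appears. The opening paragraph makes finding individual drivers of response part of the overarching objective, but the only text on how is "Planned analysis: consider analytic approaches that will allow for identification of individual-level characteristics".

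**The concern.** A SMART re-randomises non-responders so that whole strategies can be compared and tailored. If the SAP is followed as written, no strategy is estimated and the tailoring question has no model, outcome or variable list. The smaller recruited number does not explain this, because both analyses were planned as exploratory estimation.

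Two further problems follow:

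- **The GEE.** In periods 2 and 3 a participant is on a given diet either because it worked and was kept, or because another diet failed and this one was drawn. These are different kinds of participant, and their mix differs by diet whenever diets differ in response or acceptability.
- **The regime means.** An analyst who follows Section 11 and counts each participant toward every consistent regime, without weights, will over-represent those who responded at both decisions.

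**Working it through.** **1. The design counts.** Enumerating the assignment rule in Section 11 (third code element used after response at 3 months and non-response at 6; unused diet after two non-responses) gives 12 regimes, 4 paths per regime and 21 distinct paths, as the protocol states. By response history the paths number 3 (response at both decisions) + 6 + 6 + 6 = 21. The 3 never-reassigned paths each fit 4 regimes and the other 18 each fit 2. Check: 3×4 + 18×2 = 48 = 12×4.

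The protocol's figure of at least 6 participants per regime holds for 84 with unstratified blocks of 24, since three full blocks give 3×2 = 6. At 68 the average is 68/12 = 5.7 and the guaranteed minimum is 4.

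**2. Weights.** With equal allocation, a participant who responds twice is consistent with a given regime with probability 4/12 = 1/3, and anyone else with 2/12 = 1/6. The inverse weights are 3 and 6.

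**3. Bias without weights.** Let q be the true share responding at both decisions, and G their mean outcome minus that of everyone else. Pooled without weights, their share becomes (q/3)/(q/3 + (1−q)/6) = 2q/(1+q). The bias is therefore

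[2q/(1+q) − q] × G = q(1−q)/(1+q) × G.

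The documents give neither q nor G, so both were simulated with identical diets. Assumptions: mean change −2 kg per period, baseline 90 kg (SD 13), residual SD 2.5 kg, 20% finding a diet unacceptable, weight and acceptability criteria only.

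| Between-person SD of change | q | G (kg) | Bias (kg) |
|---|---|---|---|
| 0 | 0.186 | −4.5 | 0.128 × −4.5 = −0.58 |
| 2.0 kg | 0.220 | −8.8 | 0.141 × −8.8 = −1.23 |

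This matches the range of about 0.6 to 1.25 kg, in the direction of too much weight loss. It is not a bound. With 60% unacceptability (between-person SD 2.0 kg) the bias falls to about 0.4 kg. With between-person SD 3 kg, residual SD 2 kg and 20% unacceptability it rises to about 1.8 kg. With equal response rates the shift is common to all regimes and cancels in contrasts; with unequal rates it does not. At 40% unacceptability (between-person SD 2.0 kg) q is 0.124, G is −7.8 kg and the bias −0.75 kg. Regimes starting on a 20% diet and on a 40% diet would then differ falsely by about 1.23 − 0.75 = 0.48 kg. Weighted means, and means by assigned code, are unbiased.

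**4. The GEE.** This was simulated with identical diet effects on weight and a nominal level of 0.10, using between-person SD 2.0 kg, residual SD 2.5 kg, N = 84 and 68, and 2,000 runs per setting. With equal acceptability, the test of no diet difference rejected in 11 to 12% of runs. With unequal acceptability (unacceptable to 5–60% by diet) it rejected in 15 to 18%, with false differences of about 0.3 to 0.4 kg against the least acceptable diet. The period 1 comparison in the same runs stayed at 10 to 11%. The simulated GEE used working independence and omitted site, gender, duration and the COVID indicator.

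**5. Information available.** With response rate p at each decision, assumed independent, and N = 68:

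- Consistent participants per regime: 68/6 × (1+p²) = 11.8 at p = 0.2, 12.7 at 0.35 and 14.2 at 0.5.
- Participants with a real randomised choice at 6 months (response, then non-response): 68 × p(1−p) = 10.9 at p = 0.2 and 17.0 at p = 0.5.

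**The case against.** **The SAP does use data from every randomisation.** This stands. A reader might infer that the re-randomised data are ignored. They are not: the GEE and by-period summaries analyse them by current diet. What is missing is any analysis of a regime or of the re-randomised contrast itself.

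**The protocol does not plan to compare responders with non-responders.** This also stands. Read alone, "We will compare all diet sequences (there are 12) using the same outcomes" might suggest a comparison of experienced sequences, each of which fixes the response history. With identical diets such a comparison rejected in 98 to 100% of simulated runs, and gaps of 7 to 14 kg between paths can be produced. But the number 12, the list of regime codes and the distinction between 21 sequences and 12 regimes show that codes fixed before any response are meant. ANOVA over those codes rejected in 10 to 11.5% of runs at a nominal 10%. The fault is one of wording, and the large gaps describe a misreading rather than an expected result.

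**Regime means may not be what sizes the next trial.** Protocol Section 3 lists diet-level estimates as the inputs, and the sizing method cited in Section 11 cannot be checked from the documents. No claim is made here that regime means are required for that purpose.

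**The sample is small and the pilot was not powered for everything.** This is true, and it argues for estimates with intervals. It does not justify dropping the analyses without saying so.

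**The weights are not the whole answer.** Dropout and COVID-extended diet periods need handling as well. That stands and adds to the work.

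**Conclusion.** The point holds in a limited form. The SAP specifies no regime estimate and no Q-learning although the protocol plans both, and it gives no method for its own objective on individual response. Its all-period diet effect mixes stayers with switchers and is only partly protected by randomisation. In simulation this produced modest distortion (about 0.3 to 0.4 kg), and only when acceptability differed by diet. Unweighted sharing of participants across regimes would bias regime means by about 0.6 to 1.25 kg under the main assumptions, and by about 0.4 to 1.8 kg over the wider inputs tried.

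The counts and weights follow from the protocol's rule, given equal allocation to the 12 regimes. The kilogram figures rest on assumed means, SDs and acceptability, assume no dropout, and leave out the glycaemic criteria. The documents do not support saying that the trial would answer the SMART question wrongly.

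**What to change.** 1. **Reconcile the randomisation first.** Protocol Sections 7 and 11 describe blocks of 24 over 12 regimes. The Study Design entry in the Synopsis describes blocks of 4 stratified by site, and 4 is a multiple of neither 3 diets nor 12 regimes. The weights assume equal allocation; if that did not hold, use the inverse of the actual probabilities.
2. **Add the 12 regime means to the SAP.** Count each participant toward every consistent regime, with weight 3 if never re-assigned and 6 otherwise. Give participant-level robust or bootstrap intervals and no tests. Analysis by the assigned code held in CDART is a simpler alternative: unbiased but less precise, with about 5.7 participants per regime at n=68. State how dropout and extended diet periods are handled.
3. **Carry the three-stage Q-learning into the SAP** as hypothesis-generating. Name the outcome and candidate characteristics, and maximise only over options the design offers each participant. Someone who fails twice has only one diet left.
4. **Repair or restrict the GEE.** Add response status and previous diet, or base diet comparisons on period 1 and label the all-period result descriptive.
5. **Correct the wording in Protocol Section 11** from 12 diet sequences to 12 regimes.
6. **State the fate of each protocol analysis**, including the 9-month comparison by starting diet: retained, or dropped with a reason.

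The cost is SAP text and programming, more than trivial once dropout is handled, with no new data. The price in interpretation is wide intervals, from about 12 to 14 consistent participants per regime.
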